18.2 Adverse events reporting

- *Definition of an Adverse Event (AE):* An AE is any symptom, sign, illness, or experience that develops or worsens in severity during the course of the study but does not necessarily have a causal relationship with study agent/intervention or procedures. A clinical trial adverse event is defined as any untoward medical event associated with the use of a drug or study procedure. The Investigators will determine daily if any adverse events occur during the period from enrollment (signing of the informed consent) through study day 15. Investigators will determine if the event is serious or related to the study drug. The rationale for this time window is the half-life of 2 hours for losartan and 6-9 hours for its metabolite. Even in the setting of impaired clearance, 3 days after study drug cessation is more than adequate to help to define the period at risk from losartan. Abnormal

MEDICAL PROTOCOL (HRP-590)

SHORT PROTOCOL TITLE: Randomized control trial of losartan for outpatients with COVID-19

VERSION DATE:5APR2020

results of diagnostic procedures are considered to be AEs if the abnormality:

- results in study withdrawal,
- is associated with a serious adverse event (SAE),
- leads to additional treatment or to further diagnostic tests, or
- is considered by the Investigator to be of clinical significance.

- **Definition of a Serious Adverse Event:** Adverse events are classified as serious or non-serious. An SAE is any AE that is:

- *Fatal,*
- *life-threatening,*
- *requires or prolongs a hospital stay,*
- *results in persistent or significant disability or incapacity,*
- *a congenital anomaly or birth defect, or*
- *an important medical event.*

Important medical events are those that may not be immediately life threatening, but are clearly of major clinical significance. They may jeopardize the subject, and may require intervention to prevent 1 of the other serious outcomes noted above. For example, drug overdose or abuse, a seizure that did not result in in-patient hospitalization, or intensive treatment of bronchospasm in an emergency department would typically be considered serious. Serious adverse events will be collected during the first 15 study days, regardless of the investigator's opinion of causation. Thereafter, serious adverse events are not required to be reported unless the investigator feels the events were related to either study drug or a protocol procedure.

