- ***Other clinical Outcomes that may be exempt from adverse event reporting:*** Study specific outcomes as outlined in 5.1 and 5.2 are exempt from adverse event reporting unless the investigator deems the event to be related to the study procedures (or of uncertain relationship) or if the event leads to discontinuation of study procedures. The following are examples of events that will be considered study specific clinical outcomes and will be systematically tracked through the study design. The rationale for this criteria is that adverse event reporting can be sporadic and inconsistent, so events more likely to be truly related to a study intervention are better treated by consistent tracking through the systemic design and collection of potentially related adverse events:

- Hepatic events: hepatic injury or liver dysfunction that leads to an increase from baseline in the serum level of bilirubin.
- Renal events: renal failure, renal insufficiency, or renal injury that leads to an increase from baseline in serum creatinine.
- Hematologic/coagulation events: coagulopathy, disseminated intravascular coagulation, thrombocytopenia, or thrombocytosis.
- Changes in serum sodium and potassium

- ***Scales Used to Grade Severity of Adverse Events:*** All AEs will be graded in the following manner:

- Grade 1 (Mild): Events require minimal or no treatment and do not interfere with the participant's daily activities.
- Grade 2 (Moderate): Events result in a low level of inconvenience or concern. Moderate events may cause some interference with functioning.
- Grade 3 (Severe): Events interrupt a participant's usual daily activity and may require systemic drug therapy or other treatment. Severe events are usually incapacitating.
- Grade 4 (Life-threatening): Any adverse drug experience that places the participant, in the view of the Investigator, at immediate risk of death from the reaction as it occurred (i.e., it does not include a reaction that had it occurred in a more severe form, might have caused death).
- Grade 5 (Death)

- **Scales Used Attribute Adverse Events:** The Principal Investigator will assess the relationship of all AEs to any drug or study procedure:

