- **Recording and Documentation**
 - At each contact with the subject, personnel must seek information as to discomforts or adverse experiences by specific questioning and, as appropriate, by examination. This will typically occur via phone or telemedicine due to concerns regarding infectious

contagion. Information about AEs to be recorded includes event description, time of onset, investigator assessment of severity, relationship to Study Agent(s)/Intervention(s), and time of resolution/stabilization of the event. All AEs occurring during the study period (from time of consent signing to study day 15) must be documented appropriately regardless of relationship to study products or procedures unless included on the list of clinical outcomes that may be exempt from adverse outcomes reporting as part of the study protocol and outcomes. Information on all identified AEs will be recorded within 5 days recognition, while SAEs will be reported within 24 hours in the appropriate AE module of the case report form (CRF) on Redcap.

18.3 Data Safety Monitoring: A data safety monitoring board (DSMB) has been convened and includes 4 individuals meeting the key element criteria below, and includes a biostatistician with prior clinical trials DSMB experience. The DSMB will follow the guidance as outlined in the application and the attached charter unless there is a compelling, unanticipated reason to deviate from these rules. Data regarding the primary outcome (hospitalization) will be reported to the DSMB continuously, consistent with continuous study monitoring principles. The DSMB may recommend stopping the trial early only for safety, following these guidelines:

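### Renal and sodium/potassium changes are by default exempt from adverse event reporting, and the tracking offered in exchange is one day-15 draw that no named endpoint or analysis uses

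*Combined protocol and SAP*

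**What the plan says.** **Risk.** Section 13.1 puts deteriorating renal function and electrolyte disturbance in its list of losartan's most severe risks.

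**General rule.** Under 18.2, an abnormal diagnostic result is an adverse event if, among other grounds, it "is considered by the Investigator to be of clinical significance". The paragraph on abnormal laboratory values adds results that suggest organ toxicity worse than at enrollment, and results that need active management.

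**Exemption.** A later paragraph of 18.2 begins "Study specific outcomes as outlined in 5.1 and 5.2 are exempt from adverse event reporting". Its examples include "Renal events: renal failure, renal insufficiency, or renal injury that leads to an increase from baseline in serum creatinine" and "Changes in serum sodium and potassium", along with hepatic and hematologic or coagulation events. The exemption is conditional: such outcomes are "exempt from adverse event reporting unless the investigator deems the event to be related to the study procedures (or of uncertain relationship", or unless the event leads to discontinuation. The justification is that these events "will be considered study specific clinical outcomes and will be systematically tracked through the study design".

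**Recording rule.** Still in 18.2, all adverse events from consent to study day 15 are documented regardless of relationship, "unless included on the list of clinical outcomes that may be exempt from adverse outcomes reporting". The same paragraph adds, "while SAEs will be reported within 24 hours".

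**Tracking.** Section 5.4 schedules a blood draw at day 15 (± 2 days) and names creatinine. The events table in 5.5 has one row for potassium and creatinine after randomization. Section 11.4 describes the draw as renal function testing.

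**The concern.** The laboratory harms most expected from the study drug are the ones whose recording depends on a causality judgement. Every other adverse event is recorded without one. In a blinded placebo-controlled trial, the useful safety evidence is the comparison of all events by arm, whatever each investigator thought of each case. If only a share of events is recorded, and blinding makes that share equal in both arms, the recorded risk difference is the true difference multiplied by that share. The harm then looks smaller than it is.

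The exemption would be acceptable if the promised tracking put the same information in front of the reader by arm. The question is whether the plan provides that.

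**Working it through.** The plan gives no figure of its own on this point to reproduce. The check sets its rules side by side and adds simple arithmetic.

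**1. One case under each rule.** Take a non-serious creatinine or potassium abnormality that needs active management, in a participant who is not admitted.

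| Part of 18.2 | Result |
|---|---|
| Adverse event definition; abnormal laboratory values | Adverse event, to be documented |
| Exempt list: rated related or uncertain, or leads to discontinuation | Reported |
| Exempt list: rated unlikely or not related, no discontinuation | Exempt |
| Recording paragraph | Follows the exempt list; other events are documented regardless of relationship |
| The same event, if serious | Collected to day 15 whatever the cause; reported within 24 hours |

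The loss is confined to the third row.

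**2. How wide that row is.** The attribution scale in 18.2 has five grades: definitely, probably, possibly, unlikely and not related. None is called uncertain, so the plan does not say which grades trigger the exception. The possible grade can rest largely on timing, and the not-related grade requires a documented alternative cause. Many events would therefore probably come back into reporting.

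**3. What is scheduled after randomization for participants not admitted.**

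| Exempt group | Scheduled test |
|---|---|
| Renal (creatinine) | Day-15 draw (5.4, 5.5) |
| Potassium | Day-15 draw (5.5 only) |
| Sodium | None |
| Hepatic (bilirubin) | None |
| Hematologic or coagulation | None |

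The events table is broken in the text available, so the day of the potassium and creatinine mark is taken from 5.4 and 11.4.

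**4. Timing of the draw.**
- Window: 15 − 2 = day 13 to 15 + 2 = day 17.
- Lag after a day-10 last dose: 13 − 10 = 3 days to 17 − 10 = 7 days.
- In half-lives of the metabolite (6 to 9 hours in 18.2): 3 × 24 / 9 = 8 to 7 × 24 / 6 = 28. At 8 half-lives, 0.5^8, or about 0.4%, remains.
- If the course starts a day late because of courier delivery (an assumption), the shortest lag is 2 days: 2 × 24 / 9 = 5.3 half-lives, or about 2.5% remaining.

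The draw is therefore after treatment throughout its window. It could miss a rise that occurred on treatment and then resolved.

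**5. Draw window against recording window.** Adverse event recording ends at study day 15. Of the five days in the draw window (13 to 17), two (16 and 17) fall after it.

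**6. Where the results go.** Section 3.1 has one primary endpoint and 3.2 lists seven secondary items; none is renal or electrolyte. Section 15.1 names no adverse event or laboratory analysis. The events reported continuously to the DSMB are deaths, admissions, and cardiovascular and respiratory events, and the harm trigger in 18.3 is the rate of serious events.

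**7. Population concerned.** With 15% admitted in both arms: 580 × 0.85 = 493 not admitted. With 15% against 7%: 290 × 0.85 + 290 × 0.93 = 246.5 + 269.7 = 516.2. These are the participants in whom an event could be lost, not a count of lost events.

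**8. Cross-reference.** The exemption points to outcomes in 5.1 and 5.2, which are Screening and Enrollment. Endpoints are in 3.1 and 3.2, and those contain none of the listed laboratory events.

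**The case against.** The strongest reply is that this is a general rule with a specific carve-out, which is ordinary drafting. The recording paragraph gives the order of precedence, so a site can work out which rule governs. The carve-out is conditional, and the attribution scale returns many events to reporting. Serious events are collected regardless of cause, and creatinine and potassium are measured once in everyone who returns. The stated rationale, that consistent measurement is better than sporadic event reports, is sound in principle.

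Most of this stands and narrows the point. What it does not answer is that the measurement is a single draw, covers only part of the exempt list, and leads to no named endpoint or analysis.

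Four stronger readings are tempting, and the documents do not support them.
- *That the recording paragraph omits the exceptions, so no listed event is ever recorded.* It refers to outcomes that may be exempt, which is how the conditional list is titled, so the conditions come with it.
- *That the drug is left out of the exception because it names only study procedures.* Section 12.2 counts the intervention among study procedures. The wording should be made explicit, but the drug is probably covered.
- *That hospitalization becomes exempt if 3.1 and 3.2 are meant.* Sections 18.2 and 18.3 both report it as a serious event.
- *That the day-15 results go unrecorded because the data list in 1.6 omits them.* The draw is scheduled in 5.4 and 5.5, so the omission does not show this.

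The DSMB charter is attached to the protocol but is not among the documents available. It may add laboratory review for the board, though that would not supply an analysis in 15.1.

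**Conclusion.** The concern holds in a limited form. By default, the plan exempts laboratory harms that it names as severe risks of the drug. The substitute is one post-treatment draw that covers creatinine and potassium but not sodium, bilirubin, blood counts or coagulation, and no named endpoint or analysis uses it.

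The loss is mainly non-serious events rated unlikely or not related, without discontinuation, in participants not admitted. Its size cannot be computed, because the documents give neither a rate for such abnormalities nor the share that would be rated this way. It ranges from none, if blinded investigators call every event uncertain, to every event in that group. A loss of power for safety comparisons could be inferred, but any figure would rest on assumed rates and recording shares, and the plan proposes no such test.

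The primary analysis and the capture of serious events, admissions and deaths are unaffected. The change is worth making because reported safety would otherwise be incomplete on the laboratory harms expected of the drug, and because it costs little.

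**What to change.** 1. In 18.2, delete the renal and sodium/potassium lines from the exempt list so that the general laboratory rule applies to them. Reconcile the adverse event definition, the laboratory paragraph, the exempt list and the recording paragraph. Word the remaining exceptions as *study drug or study procedures*, and say which attribution grades count as uncertain. For hepatic and hematologic events, state where they are tracked or drop the claim of systematic tracking.
2. State that a renal or potassium abnormality found at the day-15 draw, on any day of its ± 2 window, is recorded as an adverse event if it meets the general rule.
3. Name potassium with creatinine in 5.4. Add to 15.1 a by-arm table of day-15 creatinine and potassium: values, change from baseline and number missing. The baseline values exist, because 5.5 asks for both within a week of randomization.
4. Correct the reference to 5.1 and 5.2, and state that no serious adverse event is exempt.

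The cost is wording changes in 5.4, 15.1 and 18.2, some additional adverse event forms and one table. There are no new visits or tests, and the timing of the draw stays as planned, so its post-treatment timing should be stated as a limitation when the results are reported.

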19.0 Provisions to Protect the Privacy Interests of Participants

- 19.1 Protecting Privacy:* Conversations will be held in a private room whenever possible. Telephone calls will be performed one on one. The electronic consent process takes place using a secure RedCAP server that is HIPAA compliant.
- 19.2 Access to Participants:* Conduct of the study and determination of both safety and efficacy of the intervention requires access of the medical records. All study personnel undergo human subjects protection training and understand and value privacy standards set forth by HIPAA. Participants enrolled in the trial are made aware during the informed consent procedure that study personnel will be required to access this private information for trial conduct, and consent to this access prior to agreeing to participate.

20.0 Compensation for Research-Related Injury

- 20.1 Compensation for Research-Related Injury:* There is no compensation available for research related injury.
- 20.2 Contract Language:* N/A.

21.0 Consent Process

- 21.1 Consent Process (when consent will be obtained):* All subjects participating in this study or their LARs will be required to provide prospective informed consent using an eConsent platform with an accompanying phone call or video feed to conduct the consent conversation. Prior to doing so, will discuss the study with study personnel who have been specially trained in obtaining informed consent. Our team has significant experience in this process, with due consideration of vulnerable patient populations. The subject or LAR will review the eConsent in detail and have the chance to ask questions. The personnel will then ask the subject questions to ensure that they understand the information presented in the consent discussion using a teach back method. The rights and welfare of the participants will be protected by emphasizing to them that the quality of their medical care will not be adversely affected if they decline to participate in this study. A copy of the informed consent document will be available electronically to the participants during the consent conversation and a signed copy will be emailed for their records. The participants may withdraw consent at any time throughout the course of the trial (see withdrawal procedures). The eConsent forms are included in this IRB submission.

- 21.2 Waiver or Alteration of Consent Process (when consent will not be obtained):* N/A
- 21.3 Waiver of Written/Signed Documentation of Consent (when written/signed consent will not be obtained):* N/A

21.4 *Non-English Speaking Participants*: Spanish and Somali speaking persons, who represent the vast majority of non-English speaking patients in the study hospitals and clinics, will be included as described above.

21.5 *Participants Who Are Not Yet Adults (infants, children, teenagers under 18 years of age)*: These patient groups will be excluded per the study protocol. If logistical and scientific concerns can be adequately addressed, we will submit a revised application with an ethical framework, scientific support, and logistical considerations.

21.6 *Cognitively Impaired Adults, or adults with fluctuating or diminished capacity to consents*: The enrollment of these patients will necessarily be affected by the location of presentation and timing of assessment. The identification of patients who lack consent capacity will not be possible in ED patients discharged or in patients presenting to drive-through clinics in this study since capacity assessments, such as the UBACC or the MacArthur Competence Assessment tool, are difficult to conduct over telemedicine or the phone, and methods of administering capacity screening tools in these settings have not yet been validating. Patients screened in the ED still physically present could be enrolled. To establish capacity in this setting, the MacArthur Competence Assessment tool will be administered by trained study personnel. If the patient lacks capacity, a LAR may provide consent for these participants on their behalf. For adults unable to consent, consent will be obtained from a legally authorized representative in the following order of priority consistent with Minnesota State Law: health care agent previously assigned via a health care power of attorney, spouse, parents, adult children, and then adult siblings. An incapacitated adult who has a court appointed guardian would require permission of the court for enrollment, and these participants will be excluded practically from the trial.

21.7 *Adults Unable to Consent*: These patients will be evaluated using the same process as 21.6, and may be eligible for consent via an LAR if physically present in the ED.

21.8 *Assent and dissent in adults with fluctuating or limited mental capacity*:

- *Assent*: If patients might have capacity, we use the MacArthur Competence Assessment Tool for Clinical Research. If they do not reach the pre-specified threshold for capacity, we seek from an LAR. We do not seek further assent, as these patients are frequently intubated, delirious, or medically sedated
- *Dissent*: However, even if the LAR consents to the trial, if the patient is awake and alert, but dissent, we will exclude the patient.

23.0 Multi-Site Research

23.1 *Study-Wide Number of Participants:* 580

23.2 *Study-Wide Recruitment Methods:* N/A

23.3 *Study-Wide Recruitment Materials:* Study brochures (attached) will be made available at all sites.

23.4 *Communication Among Sites:*

23.5 All sites have the most current version of the protocol, consent document(s), and, when applicable, HIPAA authorization.

- All required approvals (initial, continuing review, and modifications) have been obtained at each site (including by the site's IRB of record).
- All modifications have been communicated to sites, and approved (including approval by the site's IRB of record) before the modification is implemented.
- All engaged participating sites will safeguard data, including secure transmission of data, as required by local information security policies.
- All local site investigators conduct the study in accordance with applicable federal regulations and local laws.
- All non-compliance with the study protocol or applicable requirements will be reported in accordance with university or local policy.
- All other reportable events in accordance with university or local policy

23.6 *Communication to Sites:* Personnel from all sites will participate in monthly progress meeting calls, which will include discussion of any problems including reportable events, interim results, and completion of the study. More frequent communications may be planned, as becomes necessary.

24.0 Coordinating Center Research: N/A

25.0 Resources Available

25.1 Resources Available: It is difficult to estimate how many patients will develop COVID-19 in Minneapolis; however, given estimates from other countries it is likely to be 1000's if the virus is not contained.

The study PIs and research team will contribute at least 20% of their research time towards conducting and completing this study, we will leverage the rich resources of the UMN SIREN network hub and HCMC emergency department research infrastructure (of note, [name] is research director at HCMC, as well as associate research director at the University of Minnesota). In total across sites, this include >8 FTE of highly trained research nurses, coordinators, and research assistants across sites managed by the co-I plus an additional on-call pool of 8 additional trained associates providing 24/7 coverage for this and other studies. In addition, more personnel are available if funds are released for conduct of this study. All study members have completed all required responsible conduct in research coursework and have extensive research experience. The research team is built for mobile, multi-site enrollment in time-sensitive emergency care research, and has been a consistent top enroller in the NIH supported emergency care SIREN, StrokeNET, NETT, and PETAL clinical trial networks for years.

